### 5.7 Premature Withdrawal from Study Participation

At any time, participants may withdraw from the study (i.e., withdraw consent to participate) at their own request. Participation in the study may be discontinued at any time at the discretion of the Investigator and in accordance with his/her clinical judgment. No disadvantage will arise for any participant who withdraws consent for participation at any time or who is withdrawn from the study by the Investigator.

Reasons for discontinuation from the study will be recorded on the appropriate page of the CRF in any case and may include the following:

- Participant's request for withdrawal
- Investigator's decision that discontinuation is in the best interest of the participant
- Participant is lost to follow-up

Participants who elect to stop treatment will be asked to complete at minimum, follow-up spirometry. Any participant who discontinues treatment for medical reasons, e.g. because of adverse events (AEs) or clinical laboratory abnormalities, should be followed up at medically appropriate intervals in order to evaluate the course and to ensure reversibility or stabilization of the abnormality or event. If a participant fails to return for a scheduled visit, a documented effort must be made to determine the reason. This information should be recorded in the study records.

Participants whose clinicians feel that an escalation in their baseline therapy is warranted will be allowed to receive up to 14 days of increased dose of prednisone.

If at the end of that time, they still require an increased dose of prednisone, they will remain in the study and data collected as outlined in the events table, however, only their last Pulmonary Function Tests collected prior to increasing the dose of prednisone will be used for analysis.

Participants will not be allowed to begin on a new immunosuppressive drug for their sarcoidosis during the course of the study. Since these drugs take six months to become effective, this does not increase the risk to the patient. If the patient wishes to start a new therapy, they will be considered a treatment failure and they will be asked to come in to complete the end of study visit, which is the same as the month 4 visit.

## 6. Visit Specific Procedures

The following assessments will provide the basis for assessing protocol compliance and safety as well as differences between study arms for multiple efficacy variables. Data for each of the variables will be

recorded as shown below and in the Time-Events schedule (**Appendix B**), or until death or study withdrawal.

### 6.1 Screening Visit 1 Assessments

- Consent Participant
- Demographic and Enrollment Data
- Pertinent Medical History (including comorbidities and current medication list)
- Physical Examination (including height, weight and gender)
- Urine Pregnancy Test (if female of childbearing potential)
- Screening Labs; Complete Metabolic Panel (CMP) including: sodium, potassium, HCO3, creatinine, glucose, calcium, BUN, total bilirubin, total protein, ALT, AST\*
- Complete Blood Cell Count including: WBC, RBC, hemoglobin, hematocrit and platelet count\*
- Immune responses against mycobacterial ESAT-6 (T cell recognition assay)  
\*If this testing was done within the 14 days prior to this visit, these results may be used for this visit.

A screening log will be maintained for those potential participants who are contacted for screening in this study. This log will include the reason if the patient is not enrolled. Data entry into REDCap of screening log data will not include patient identifiers. Clinical sites will maintain the screening log in their research files.

### 6.2 Screening Visit 2 Assessments

- Spirometry (FVC, FEV1) and DLCO if possible
- Chest X ray\*
- Six Minute Walk Test (6MWT)\*\*, including Borg Dyspnea Score and oxygen saturation (there should be two 6MWTs performed at least one hour apart to confirm reproducibility of baseline assessments) (Exception: if participant is experienced with the 6MWT only 1 is necessary at baseline.)
- St. George's Respiratory Questionnaire
- King's Sarcoidosis Questionnaire
- Fatigue Assessment Score (FAS)

\*If CXR was done within the 30 days prior to this visit, this result may be used for this visit.

\*\*There should be two tests performed at least one hour apart to confirm reproducibility of baseline assessments.

### 6.3 Baseline Visit Assessments

After confirming eligibility (ESAT-6 eligible and inclusion and exclusion criteria are met) **and** prior to dosing, the following procedures and assessments will be performed:

- Bronchoscopy with bronchoalveolar lavage (BAL) for T cell study\*
- Randomization (Site Pharmacy)

\*The bronchoscopy should be conducted after the 6MWT to avoid any confounders of outcome. Site-specific routine bronchoscopy procedures, such as sedation and lavage volume, should be followed; shipping of  $\geq 60$ cc of complete BAL fluid should be shipped overnight at room temperature to the [name] lab in the sample collection tubes provided. If 60cc are not available, each site should send what is available. If the baseline bronchoscopy is associated with adverse events, inability to obtain sufficient specimen, patient refuses, a second bronchoscopy should be omitted.

The assessment weeks will be as follows:

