### 4.2 Special Populations

The demographic profiles of Vanderbilt show that the aggregate patient population contains representative proportions of minorities and women. Recruitment of minorities and women will be monitored by the research coordinator. If necessary, additional recruitment efforts will be made with collaborators to ensure that the aggregate patient sample contains appropriate gender and minority

subsets. Pregnant women will be excluded because of the lack of safety data for antimycobacterial therapy use during pregnancy.

This study will not enroll prisoners. However, it is possible that a participant will be incarcerated after enrollment. If an enrolled individual is incarcerated, then study medications will be stopped and the participant will be treated for pulmonary sarcoidosis according to the standards of the institution in which s/he is incarcerated. While incarcerated, individuals will not be followed in the study. When the individual is no longer incarcerated, study treatment and/or study follow-up may continue, at the discretion of the investigator.

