##### 4.5.2 Exclusion Criteria:

1. Inability to obtain consent
2. Age less than 18 years of age
3. Female participants of childbearing potential not willing use one of the following methods of birth control for the duration of the study and 90 days after study completion: condoms, sponge, foams, jellies, diaphragm, or non-hormonal intrauterine device, a vasectomized sole partner or abstinence. **Note: Oral contraceptive pills are not effective birth control when taking rifamycin.** Females of childbearing potential must have a negative urine pregnancy test at screening visit

4. FVC predicted value is < 45%.
5. End-stage fibrotic pulmonary disease
6. Significant underlying liver disease
7. Allergy or intolerance to any of the antibiotics within the CLEAR regimen.
8. Allergy or intolerance to albuterol
9. Poor venous access for obtaining blood samples
10. History of active tuberculosis, close contact with a person with active tuberculosis within the 6 months prior to the screening visit or has a positive PPD.
11. Significant disorder, other than sarcoidosis, that would complicate the treatment evaluation, such as respiratory, cardiac, neurologic, musculoskeletal or seizure disorders.
12. Use of an investigational drug within 30 days prior to screening or within 5 half-lives of the agent, whichever is longer.
13. Currently receiving >40mg prednisone.
14. ALT or AST  $\geq 5$  times upper limit of normal (ULN)
15. Leukopenia, as defined by WBC <3.0 cells/mm^3 or absolute neutrophil count <1000 mm^3
16. Breast feeding.
17. Color perception impairment as defined by the inability to differentiate colors per personal history or history of optic neuritis from any cause, including from sarcoidosis.
18. If patient is on immunomodulators, they must be on regimen for  $\geq 3$ -month period and on a stable dose for  $\geq 4$  weeks.
19. Family or personal history of long QT interval
20. Most recent nuclear medicine scan or echocardiogram (if done), demonstrating cardiac ejection fraction <35%
21. Participant has persistent or active infections requiring hospitalization or treatment with antibiotics, antiretrovirals, or antifungals within 30 days of baseline. Minocycline and doxycycline are not considered antibiotics when used to treat sarcoidosis.

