## 7. Statistical Considerations

### 7.1 Statistical Methods

#### 7.1.1 Analysis of Primary Endpoint

The comparison between CLEAR and placebo arms will be made using the Students's t-test. Normality of the primary endpoint will be examined using Kolmogorov-Smirnov test. If normality is violated, the comparison between CLEAR and placebo arms will be made using the Wilcoxon rank sum test.

The primary endpoint of this study is the arithmetic difference between %FVC predicted value measured at baseline and week 16 for each patient randomized. For analysis purposes, we define the week 16 post-randomization %FVC predicted value measurement at the value closest to 16 weeks from randomization within a window of 12 weeks to 20 weeks from randomization. This more accurately represents the data collected at 16 weeks on study due to the variability of visit schedules resulting from staggering the start of study drugs and patient scheduling. To understand the trajectory of improvement with CLEAR therapy, we will also be measuring the %FVC predicted value at weeks 4 and 8. If the improvement is linear in time, the rate of improvement (slope of change) may be reported as a secondary endpoint in the study.

This analysis is an exploratory analysis. Mixed effect models will be used to analyze these repeated measures with a random subject effect and with the treatment (CLEAR versus placebo) and the time trend (baseline, week 4, week 8, and week 16) as fixed effects. For the error covariance, we will use autoregressive model of order 1 [AR(1)] or other plausible covariance structures. The focus of this study will be the treatment effect and the time trend of the endpoint; however, mixed effect models also provide the flexibility of controlling for and evaluating covariates such age, race, and gender.

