## Appendix A: Time and Events Schedule

Data Collection: Table. CLEAR II Trial Assessments							
Event	Screening Visit 1	Screening Visit 2	Baseline Visit	Week 4 Visit ± 7 days	Week 8 Visit ± 7 days	Week 16 Visit ± 7 days	Week 24 Visit ± 7 days
Consent	X						
Medical History	X						
Physical Exam	X			X	X	X	X
Pregnancy test (if female)	X			X	X	X	
Blood Chemistry (CMP  ; CBC  )	X			X	X	X	
T cell recognition assay	X			X	X	X	X
Spirometry Test/DLCO		X		X	X	X	X
Chest X-ray		X				X	
6MWT  /Borg Dyspnea Score		X*		X	X	X	X
Questionnaires		X				X	
Bronchoscopy			X			X	
Compliance evaluation				X	X	X	
Adverse Events				X	X	X	X
CLEAR II Therapy Initiation			X				

\* 6MWT should be done 2 times (1 hour apart) at this visit, remaining visits, only once (Exception: if participant is experienced with the 6MWT only 1 is necessary at baseline.)

CMP=Complete metabolic profile; CBC=Complete blood count; 6MWT=Six minute walk test

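### No test is repeated at the Baseline Visit and no interval ties screening to randomization, so the pre-dose pregnancy test and the baseline FVC have no upper limit on their age at first dose

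*Combined protocol and SAP*

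**What the plan says.** **Baseline Visit.** Section 6.3 requires eligibility to be settled before any procedure ("After confirming eligibility (ESAT-6 eligible and inclusion and exclusion criteria are met"). It then lists two items: "Bronchoscopy with bronchoalveolar lavage (BAL) for T cell study" and randomization. In Appendix A the Baseline column is marked only for bronchoscopy and therapy initiation.

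**Pregnancy.** Section 6.1 places the "Urine Pregnancy Test (if female of childbearing potential" item at Screening Visit 1. The criterion in section 4.5.2 refers to that same visit: "Females of childbearing potential must have a negative urine pregnancy test at screening visit". Section 4.2 gives the reason: "Pregnant women will be excluded because of the lack of safety data for antimycobacterial therapy use during pregnancy". A positive test ends treatment under section 5.6, and section 12.1 names pregnancy as a stop point. The Appendix A row "Pregnancy test (if female" is marked at Screening Visit 1 and at weeks 4, 8 and 16.

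**FVC.** Section 6.2 places "Spirometry (FVC, FEV1) and DLCO if possible" at Screening Visit 2. The next spirometry is at week 4. Section 7.1.1 defines the primary endpoint as "the arithmetic difference between %FVC predicted value measured at baseline and week 16". It gives the week 16 value a window of 12 to 20 weeks from randomization and gives the baseline value none.

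**Intervals.** Two allowances for earlier results exist: 14 days for chemistry and blood count (6.1) and 30 days for the chest X-ray (6.2). Both count back from a screening visit.

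**The concern.** A patient attends three pre-dose visits and must have an ESAT-6 result before the third, so some gap between screening and first dose is built into the design. The plan puts no ceiling on it.

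Two things depend on that gap. The first is safety. The protocol excludes pregnant women, stops treatment on pregnancy and retests three times after dosing starts, yet it schedules no test at the visit where therapy begins. A site could follow the schedule exactly and dose a woman whom section 4.2 means to keep out.

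The second is the primary endpoint. One end of the FVC difference is tied to randomization by an explicit window and the other is not. Whatever FVC does between Screening Visit 2 and first dose is folded into each patient's change score.

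**Working it through.** **1. Does any passage close the gap?**

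| Possible safeguard | Where | Does it limit the age at first dose? |
|---|---|---|
| Eligibility confirmed before Baseline procedures | 6.3 | No. The pregnancy criterion is met by a negative result at the screening visit (4.5.2), whenever that was. |
| 14-day allowance | 6.1 | No. It covers chemistry and blood count only, and counts back from Screening Visit 1. |
| 30-day allowance | 6.2 | No. It covers the chest X-ray only, and counts back from Screening Visit 2. |
| Walk test before bronchoscopy | 6.3 | No. It sets an order, not an interval. |
| 30-day look-back to baseline | 4.5.2, exclusion 21 | It is tied to baseline, but concerns infection and anti-infective treatment only. |

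None limits the age of the pregnancy test or of the FVC.

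**2. When would a conception between Screening Visit 1 and Baseline be found?** The next scheduled test is at week 4 ± 7 days, that is, day 28 − 7 = 21 to day 28 + 7 = 35.

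**3. Which FVC is the baseline?** Section 6.8 lists FVC at baseline, but the Baseline Visit has no spirometry. By the schedule it must be the Screening Visit 2 value.

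**4. The plan's own sample size.** The inputs from section 7.3 are SD 7.7, difference 5 points, power 90% and dropout 20%. The significance level is not stated; two-sided 0.05 is assumed.

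- Standardized difference: 5 / 7.7 = 0.649.
- The noncentral t solution is 50.8, so 51 per arm, with power 0.901 at 51.
- Dropout: 51 / 0.80 = 63.75, so 64 per arm and 128 in total.

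The plan's figures reproduce.

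**5. Effect of pre-dose drift on power.** Suppose drift between Screening Visit 2 and first dose varies between patients with SD d, independently of later change, and that 7.7 contains none of it. Then

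SD of change = √(7.7² + d²)

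The values of d are assumptions; the documents give neither a drift variance nor a typical gap.

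| d | SD of change | Variance ratio | Power at 51 per arm | Per arm for 90% power |
|---|---|---|---|---|
| 0 | 7.70 | 1.00 | 0.90 | 51 |
| 2 | √(59.29 + 4) = 7.96 | 63.29 / 59.29 = 1.07 | 0.88 | 55 |
| 3 | √(59.29 + 9) = 8.26 | 68.29 / 59.29 = 1.15 | 0.86 | 59 |

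**6. Bias.** The baseline FVC precedes randomization, so drift has the same expected distribution in both arms. The difference between arms stays unbiased; the mean change within each arm does not isolate change on treatment.

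**The case against.** Several stronger readings are tempting, and the documents do not support them.

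- **That nothing is checked before dosing.** Section 6.3 does require eligibility to be confirmed, and exclusion 21 looks back from baseline. What is missing is a repeat test.
- **That the results will in practice be very old.** Only the ceiling is missing. Both tests are done at study visits, and the allowances for earlier results do not extend to them. The documents give no ESAT-6 turnaround or usual screening length, so the real gap is unknown.
- **That the omission causes up to 35 days of exposure.** Day 35 is the latest in-window week 4 visit. A baseline test would catch only conceptions that had occurred and were detectable by then. Later ones would wait for week 4 in any case, and the plan accepts eight weeks between the tests at weeks 8 and 16. The contraception requirement in exclusion 3 also lowers the risk. Under the staggered start in section 5.3, only two of the drugs begin on day 0.
- **That old FVC values bias the result, or that entry guarantees falling FVC.** Drift precedes randomization. The progression criterion can also be met by imaging or dyspnea alone.

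The variance calculation has limits too. The SD of 7.7 comes from 34 bosentan-treated participants whose baseline timing is not given. It may already contain such drift, in which case adding more counts it twice. Finally, section 11.2 refers to a Manual of Operations and Procedures, which might set visit windows; that cannot be checked here.

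These points limit the size of the concern. They do not supply the missing interval, and they do not show that the exclusion is verified at dosing.

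**Conclusion.** The point stands in a limited form. Read together, sections 4.5.2, 6.1 to 6.3 and Appendix A set no upper limit on the age of the pregnancy test or the baseline FVC at first dose. The pregnancy exclusion and stop point are therefore not matched by the schedule at the visit where therapy starts. How often this would matter cannot be estimated from the documents.

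For the primary endpoint the loss is modest: about 2 to 4 percentage points of power under the assumed drift SDs of 2 and 3, with no bias between arms. This rests on independent drift, two-sided 0.05 and a planned SD free of pre-dose drift. It still deserves correction, because the planned size meets 90% power with almost nothing to spare (0.901). The trial is not invalid without the change.

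**What to change.** 1. **Pregnancy test.** Reconcile sections 4.2, 4.5.2 and 12.1 with the visit schedule by adding the urine test already in use to section 6.3 and to the Baseline column of Appendix A. The clinical handling of the result is for the sponsor to state.
2. **Baseline FVC.** In section 7.1.1, define baseline percent predicted FVC as the last value before randomization that falls within an interval chosen and stated by the sponsor, as is already done for week 16. Where screening runs beyond that interval, repeat spirometry before the bronchoscopy. No particular length is proposed, since the documents give no basis for one.

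The cost is one urine test per woman of childbearing potential and an occasional repeat spirometry. The text changes are a line in section 6.3, a mark in Appendix A and a definition in section 7.1.1, with provision for the repeat spirometry.

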### 6.4 Therapy Week 4 Visit Assessment (+/- 7 days)

Week 4 assessments should be completed as near week 4 as possible +/- 7 days.

- Physical Assessment (record any new signs, symptoms, adverse events since last visit)
- Urine pregnancy test, if female of childbearing potential
- Complete metabolic profile and complete blood count
- Blood for T cell recognition of mycobacterial virulence factors and T cell function
- Spirometry (record FVC and FEV1 data pre and post bronchodilator, if available) and DLCO (if available)
- One 6MWT, Borg Dyspnea Score and oxygen saturation
- Review of medication diary and pill count/reconciliation
- Assess for AEs and record

#### 6.5 Week 8 Visit Assessment (+/- 7 days)

Week 8 assessments should be completed as near week 8 as possible +/- 7 days.

- Physical Assessment (record any new signs, symptoms, adverse events since last visit)
- Urine pregnancy test, if female of childbearing potential
- Complete metabolic profile and complete blood count
- Blood for T cell recognition of mycobacterial virulence factors and T cell function
- Spirometry (record FVC and FEV1 data pre and post bronchodilator, if available) and DLCO (if available)
- One 6MWT, Borg Dyspnea Score and oxygen saturation
- Review of medication diary and pill count/reconciliation
- Assess for and record AE's

#### 6.6 Week 16 Visit Assessment (+/- 7 days)

Week 16 assessments should be completed as near week 16 as possible +/- 7 days.

- Physical Assessment (record any new signs or symptoms since last visit)
- Urine Pregnancy test, if female of childbearing potential
- Complete metabolic profile and CBC
- Blood for T cell recognition of mycobacterial virulence factors (ESAT-6) and T cell function
- Spirometry (record FVC and FEV1 data pre and post bronchodilator, if available) and DLCO (if available)
- Bronchoscopy with Bronchoalveolar Lavage (BAL) for T cell study
- One 6MWT and oxygen saturation and Borg Dyspnea Score
- St. George's Respiratory Questionnaire
- Fatigue Assessment Score (FAS)
- Kings Sarcoidosis Questionnaire
- Review of medication diary and pill count/reconciliation
- Assess for and record AE's;

#### 6.7 Week 24 Visit Assessment (+/- 7 days)

Week 24 assessments should be completed as near week 24 as possible +/- 7 days.

- Physical Assessment (record any new signs or symptoms since last visit)
- Blood for T cell recognition of mycobacterial virulence factors (ESAT-6) and T cell function
- Spirometry (record FVC and FEV1 data pre and post bronchodilator, if available) and DLCO (if available)
- One 6MWT and oxygen saturation and Borg Dyspnea Score
- Assess for and record AE's

This visit should be at least 168 days following the date of the first dose of study drug, but can be later, if contact with the participant is intermittently lost to follow-up. Document all attempts to contact the participant in the case report form. Document the date of last contact.

## 6.8 Assessments for Data Collection

Data will be collected to assess the following endpoints:

- FVC percent predicted, FVC, FEV1 at baseline, week 4, week 8, and week 16
- Radiographic assessment of sarcoidosis lung disease using the Muer scoring system at baseline, week 4, week 8, and week 16.
- Change in 6 minute walk distance and oxygen saturation from baseline to 16 weeks.
- Change in questionnaires from baseline to 16 weeks.
- Decrease in peripheral and pulmonary T cell response to mycobacterial antigens between baseline and 16 weeks, as well as T cell function assays.
- Adverse events, assessments and laboratory results for safety analysis.
- Standard of care therapies.

## 7. Statistical Considerations

### 7.1 Statistical Methods

#### 7.1.1 Analysis of Primary Endpoint

The comparison between CLEAR and placebo arms will be made using the Students's t-test. Normality of the primary endpoint will be examined using Kolmogorov-Smirnov test. If normality is violated, the comparison between CLEAR and placebo arms will be made using the Wilcoxon rank sum test.

The primary endpoint of this study is the arithmetic difference between %FVC predicted value measured at baseline and week 16 for each patient randomized. For analysis purposes, we define the week 16 post-randomization %FVC predicted value measurement at the value closest to 16 weeks from randomization within a window of 12 weeks to 20 weeks from randomization. This more accurately represents the data collected at 16 weeks on study due to the variability of visit schedules resulting from staggering the start of study drugs and patient scheduling. To understand the trajectory of improvement with CLEAR therapy, we will also be measuring the %FVC predicted value at weeks 4 and 8. If the improvement is linear in time, the rate of improvement (slope of change) may be reported as a secondary endpoint in the study.

This analysis is an exploratory analysis. Mixed effect models will be used to analyze these repeated measures with a random subject effect and with the treatment (CLEAR versus placebo) and the time trend (baseline, week 4, week 8, and week 16) as fixed effects. For the error covariance, we will use autoregressive model of order 1 [AR(1)] or other plausible covariance structures. The focus of this study will be the treatment effect and the time trend of the endpoint; however, mixed effect models also provide the flexibility of controlling for and evaluating covariates such age, race, and gender.

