### 5.1 Blinding and Randomization

Participants will be randomized to either CLEAR therapy or placebo at a ratio of 1 to 1 stratifying by site and use of prednisone  $\geq 10$  mg or not and using a permuted-block randomization algorithm with random block sizes. Randomization schedules will be generated by a statistician who is not involved with the conduct of the clinical trial. The Vanderbilt Investigational Pharmacy will provide each site with the study drugs and site-specific treatment assignments. The placebos and colored capsules will be obtained by each site. Pills of identical appearance containing antibiotics (each a different color) or placebo will be prepared and dispensed by each site's study pharmacy. A participant's treatment assignment will only be revealed outside the pharmacy if a clinical emergency necessitates unblinding their treatment or if requested by the DSMB. Neither participants, clinical providers, nor those influencing recruitment decisions or interpretation of data will be aware of the treatment that is assigned or the order that treatments will be allocated.

Patients will be considered enrolled upon randomization. Patients receiving any amount of study drug will be considered treated. Patients discontinued from receipt of study drug for any reason, will continue to follow all other protocol requirements for the entire 180 day study period to the extent that the informed consent is still active.

Only the investigational pharmacists and the DSMB will be unblinded to randomization assignments. There are safety issues associated the CLEAR regimen; for example, levaquin and prolongation of the QT interval. If there is a significant safety issue thought related to study drug, all four study drugs within the regimen should be stopped and the patient followed until stabilization or resolution of this issue. Efforts will be made to unblind only individuals not associated with the research and who need to know, such as an attending physician. Should un-blinding of an individual become necessary during the study, the investigator at the clinical site should contact the Vanderbilt Clinical Coordinating Center (CCC) for approval and specific unblinding instructions.

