#### 7.1.2 Approaches to the Analysis

The following 2 approaches will be used for the analyses:

- **Intention-to-Treat** All patients with a post-treatment endpoint measurement will be included. This will be considered the primary analysis and performed for all endpoints.
- **Per Protocol** This will be performed as a secondary analysis for the primary endpoint only. A patient who is identified as a major protocol violator will not be included. Protocol violators will be considered as follows: 1) Realize that patient did not meet Inclusion Criteria after enrolled into study; 2) Find an Exclusion criteria after enrolled into the study; 3) Regimen was

permanently stopped before 4 weeks; 4) Exacerbation requiring greater than 2 weeks of prednisone escalation. Major protocol violators will also be defined based on criteria that will be identified prior to unblinding the database.

**7.1.3 Multiplicity:** Since there is only 1 primary comparison for 1 primary endpoint for each study aim, and other comparisons are secondary and supportive, no multiplicity adjustment will be applied.

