## 7.2 Randomization

Participants will be randomized to either CLEAR therapy or placebo at a ratio of 1 to 1 stratifying by site and use of prednisone  $\geq 10$  mg or not and using a permuted-block randomization algorithm with random block sizes. Treatment assignments of the study will be made using separate randomization schedules for each of the three participating sites. The randomization schedule will be prepared by the DCC prior to initiation of patient recruitment. Randomization schedules will be generated by a statistician who is not involved with the conduct of the clinical trial. All randomization schedules will be generated using R, will remain confidential and known only by the site pharmacists until the database is locked and randomization assignments no longer must be blinded. Randomization marks the patient's official entry into the Study. Once a participant has been started on the assigned study treatment, efforts will be made to conduct all evaluations irrespective of whether the participants complete the study treatment regimen or not, or how well the participants complies with the study treatment regimen. These efforts should continue until termination of the study. Data collections will continue even if medication must be stopped.

For the intention to treat analysis, participants will be considered treated when the first study drug is taken, regardless of the amount of study drug they receive. Participants discontinued from receipt of

study drug for any reason, will continue to follow all other protocol requirements for the entire study period to the extent that the informed consent is still active.

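### The primary t-test on change in FVC % predicted is valid, but omitting baseline FVC and the randomization strata can give up a little precision from data already collected

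*Combined protocol and SAP*

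**What the plan says.** Section 7.1.1 defines the primary endpoint as week 16 minus baseline FVC % predicted and sets the test: "The comparison between CLEAR and placebo arms will be made using the Students's t-test". A pre-test follows, "Normality of the primary endpoint will be examined using Kolmogorov-Smirnov test", and then a switch: "If normality is violated, the comparison between CLEAR and placebo arms will be made using the Wilcoxon rank sum test". No covariate enters either branch.

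Randomization is described in section 5.1 as "stratifying by site and use of prednisone" (10 mg or more, or not). Section 7.2 repeats this and adds "separate randomization schedules for each of the three participating sites". Baseline spirometry is done at Screening Visit 2 (section 6.2), before randomization.

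The only model for FVC is the repeated-measures mixed model in section 7.1.1. The section notes that "mixed effect models also provide the flexibility of controlling for and evaluating covariates such age, race, and gender". That model is labelled exploratory and does not name the strata.

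Section 7.1.2 defines the primary analysis set: "All patients with a post-treatment endpoint measurement will be included". The section on analysis of secondary endpoints carries the primary methods over to all continuous secondary endpoints.

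**The concern.** A change score fixes the coefficient of baseline at one. If patients who start low tend to gain more than patients who start high, for instance through regression to the mean, part of the spread in change is predictable from baseline. A fitted slope removes that part; the t-test leaves it in the error term. Likewise, stratified randomization balances the arms on site and prednisone, but a test that ignores those factors counts their variation as noise.

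At stake are the width of the confidence interval and a few points of power. This matters more if completers fall short of 51 per arm; section 7.3 reports a 30% drop rate in Phase I against the 20% planned here.

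**Working it through.** **Inputs.** From section 7.3: SD of change 7.7, difference 5, 51 completers per arm, 90% power, 64 enrolled per arm. Assumed: two-sided 5% level (not stated, but it reproduces 51); baseline SD 10, 15 or 20; equal SDs at baseline and week 16; normal errors unless noted.

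**Step 1: the plan's own figure.** The standard error is 7.7 × √(2/51) = 1.525 and the noncentrality is 5/1.525 = 3.28 on 100 degrees of freedom. Power is 90.1%. With 20% dropout, 51/0.80 = 63.75, so 64 per arm. Both figures reproduce.

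**Step 2: add baseline.** With equal SDs, the error variance relative to the change score is 1 − 7.7²/(4 × SD_base²). Multiply by 1 + 1/(2n − 4), which is 1.0102 at n = 51, for estimating the slope.

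| Baseline SD | Ratio | Ratio × 1.0102 | Power at 51/arm | t-test n per arm with same power |
|---|---|---|---|---|
| 10 | 0.852 | 0.861 | 93.8% | about 59 |
| 15 | 0.934 | 0.944 | 91.7% | about 54 |
| 20 | 0.963 | 0.973 | 90.9% | about 52 |

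At 45 per arm (64 × 0.70 = 44.8), the t-test has 86.1% power; with baseline it is 90.7%, 88.0% and 87.0%.

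**Step 3: the lower limit.** If change is unrelated to baseline, the slope gains nothing. With the SD of change held at 7.7, this happens when the week 16 SD is √(SD_base² + 7.7²) = 12.6, 16.9 or 21.4. The model then costs only the factor 1.0102 in variance, about 0.5% in standard error. Exclusion 4 in section 4.5.2 ("FVC predicted value is < 45"%) sets a floor and there is no ceiling, so a wide baseline spread, and a gain near the low end, is plausible.

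**Step 4: add the strata.** Simulation used 102 patients, 3 sites, prednisone yes in 40% (assumed), permuted blocks of 2 and 4, and 20,000 trials per cell. Entries are power for the t-test, then the full model, at baseline SD 10 / 15 / 20.

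| Strata share of variance in change (assumed) | t-test | Full model |
|---|---|---|
| 0% | 90.2 / 89.9 / 90.5 | 94.0 / 91.6 / 91.3 |
| 5% | 90.7 / 90.7 / 91.0 | 95.0 / 92.9 / 92.6 |
| 10% | 91.3 / 91.4 / 91.0 | 96.3 / 94.2 / 93.4 |

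Reading down the full-model column, the strata add 1.0 to 1.3 points at 5% and 2.1 to 2.6 points at 10%. If they explain nothing, including them costs 0.2 points or less. At a 0% share the 95% interval half-width is 3.02 for the t-test and 2.80, 2.94 or 2.98 for the model. Type I error of the t-test is 4.4% to 4.5% at a 5% share and 3.6% to 4.1% at 10%, so ignoring the strata is conservative.

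**Step 5: compare with the planned two-step rule.** The plan is the t-test plus the Wilcoxon fallback. Simulated power at 51 per arm, baseline SD 15, strata share 0, with the Kolmogorov-Smirnov test on pooled residuals, corrected for the estimated mean and SD, at an assumed 5% level:

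| Shape (assumed) | Baseline model alone | Planned two-step rule |
|---|---|---|
| Normal | 91.3% | 90.2% |
| t(5) | 91.9% | 93.2% |
| t(3) | 92.0% | 98.0% |
| Skewness 1 | 91.5% | 92.1% |

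Repeat runs moved these figures by up to about a point, so only the t(3) gap is large. With the uncorrected test, the model is level or slightly ahead except under t(3).

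**Step 6: does the gate's missing detail matter?** Its level, version and sample (pooled or by arm) are not stated. For normal, t(5), t(3) and skewness 1, the corrected and uncorrected pooled versions pick different tests in 5%, 23%, 41% and 50% of trials. The significance decision differs in only 0.3%, 2.2%, 3.3% and 3.0%. Type I error of the two-step rule is 4.8% to 5.4%.

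**The case against.** The strongest reply is that nothing is broken: the test is valid, the sample size is right for it, and an amendment is a real cost for an uncertain gain. Most of this stands. The size of the gain rests on SDs and variance shares that the documents do not give, and it can be about zero.

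A second objection is that the relevant comparator is the two-step rule, not the t-test alone. This also stands. A model without the rank fallback can have less power than the plan under heavy tails or skewness. It is an argument for keeping the fallback, not against adjusting the t-test branch.

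Third, the 45-per-arm case may be pessimistic. Section 7.3 attributes most Phase I withdrawals to advanced disease and lists measures to improve retention, and section 7.2 continues evaluations after treatment stops. The case shows sensitivity to dropout and is not a forecast.

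Fourth, the mixed model already contains baseline and allows covariates. It does, but it is exploratory and leaves the primary test unchanged.

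A reader might infer more: that the trial is underpowered, that the t-test is biased or inflates type I error, or that the normality gate should be removed. The documents and calculations support none of these. Power is 90.1% as planned, ignoring the strata errs on the conservative side, and the gate's missing details rarely change the decision.

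**Conclusion.** The concern holds as a modest point of efficiency. Fitting baseline adds about 0.8 to 3.7 power points at 51 per arm (90.9% to 93.8% against 90.1%) for baseline SD 20 down to 10, given normal errors and equal SDs at the two times; it adds about nothing if change is unrelated to baseline. The strata add roughly 1 to 3 points if they explain 5% to 10% of the variance in change, and cost almost nothing if they do not.

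The absence of the covariates from the primary test is certain from the text; the size of the benefit is not. Removing the rank fallback is a separate trade-off and is not supported as an improvement. Nor is there support for applying the model without a fallback to the secondary endpoints in section 3.2, which include oxygen saturation and T cell assay measures for which normality is less assured.

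**What to change.** - **Primary analysis.** In section 7.1.1, replace the t-test branch with one linear model for week 16 FVC % predicted, with treatment, baseline FVC % predicted, prednisone at 10 mg or more (yes/no) and site. Report the adjusted mean difference with its 95% CI. Because baseline is fitted, the treatment coefficient is the same whether the outcome is the week 16 value or the change, so the target remains a difference in mean change.
- **Small sites.** Fix a pooling rule before unblinding, for example that sites with fewer than 8 randomized patients form one category.
- **Fallback.** Keep the Wilcoxon test, with normality assessed on the model residuals. While amending the section, state the level and version of the Kolmogorov-Smirnov test and the estimate to be reported after a switch; the mean difference is implicit in the t-test branch, but the Wilcoxon branch names none.
- **Continuous secondary endpoints.** Use the adjusted model, with each endpoint's own baseline, in the t-test branch only, and retain the rank fallback.

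**Cost.** This needs a protocol amendment with IRB approval (section 10.1). It must be made before unblinding and documented as independent of the efficacy data shown at the 50-participant interim look (section 7.4). No new data are needed. The section 7.1.2 analysis set is unchanged, because every patient with a change score has a baseline value, a site and a prednisone stratum. With three sites the residual degrees of freedom fall from 100 to 96, and the critical t moves from 1.984 to 1.985.
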